4.11.2. Secondary clinical outcomes

Secondary clinical outcomes will be:

[figure not shown]
- Numerical Rating Scale (NRS) score - The NRS will ask patients to rate their pain intensity on an 11-point scale where 0 indicates no pain and 10 indicates worst imaginable pain. The NRS score will be collected at baseline and at all follow-up examinations, i.e., two weeks, four weeks, 12 weeks and 24 weeks after baseline. A point score change of 4 points for the NRS score corresponds to the MCID (Maughan and Lewis, 2010). Note that according to

Maughan and Lewis (2010) the NRS score is least responsive in measuring clinically meaningful change in a chronic non-specific low back pain population.

- Oswestry Low Back Pain Disability Questionnaire (OLDPDQ) score (Fairbank and Pynsent, 2000; Davidson and Keating, 2001) – The OLDPDQ score is considered the ‘gold standard’ of low back functional outcome tools. The questionnaire is composed of ten sections (addressing pain intensity, personal care, lifting, walking, sitting, standing, sleeping, sex life, social life and travelling); for each section the possible score is 5 and, thus, the total possible score is 50. The final score is calculated as $[(\text{sum of individual scores}) / 50] * 100$ (%), and is interpreted as *minimal disability* (0% to 20%), *moderate disability* (21% to 40%), *severe disability* (41% to 60%), *crippled* (61% to 80%) or *patients are either bed-bound or exaggerating their symptoms* (81% to 100%). The OLDPDQ score will be collected at baseline and at all follow-up examinations, i.e., two weeks, four weeks, 12 weeks and 24 weeks after baseline. A point score change of 8 points for the OLDPDQ score corresponds to the MCID (Maughan and Lewis, 2010).
- Patient Health Questionnaire 9 (PHQ-9) score (Kroenke et al., 2001) – The PHQ-9 will be used to assess depression. Patients will be asked how often, over the last two weeks, they had been bothered by the following problems: (i) little interest or pleasure in doing things; (ii) feeling down, depressed or hopeless; (iii) trouble falling or staying asleep, or sleeping too much; (iv) feeling tired or having little energy; (v) poor appetite or overeating; (vi) feeling bad about themselves, or that they are a failure or have let themselves or their family down; (vii) trouble concentrating on things, such as reading the newspaper or watching television; (viii) moving or speaking so slowly that other people could have noticed? Or the opposite – being so fidgety or restless that they have been moving around a lot more than usual; and (ix) thoughts that they would be better off dead or of hurting themselves in some way. For each potential problem the PHQ-9 score uses a 4-point scale where 0 = not at all, 1 = several days, 2 = more than half the days and 3 = nearly every day. The PHQ-9 score will be collected at baseline and at 12 weeks and 24 weeks after baseline.
- Lumbar curvature measurements performed on lateral lumbosacral spine radiographs – Chun et al. (2017) found a strong relationship between non-specific low back pain and decreased lumbar lordotic curvature in a recent meta-analysis based on 13 studies consisting of 796 patients suffering from non-specific low back pain and 927 healthy controls. Lateral X-rays of the lumbar spine will be taken in the standing position according to standard protocols in the literature (e.g., Chernukha et al., 1976; Marks et al., 2009; Been and Kalichman, 2014) and analyzed using Cobb’s angle, vertebral body and intervertebral

disc wedging, and facet joint angle (Fig. 3) (e.g., Been and Kalichman, 2014). Lumbar curvature measurements will be performed at baseline and at 12 weeks after baseline.

Fig. 3 (taken from Been and Kalichman, 2014). Measurements of lumbar lordosis Cobb's angle (LA), vertebral body (B) and intervertebral disc (D) wedging, and facet joint angle (F).

4.12. Blinding of therapists and assessors

- Therapists applying the treatments will not be blinded. This will be done because even when using coded “active” and “placebo” handpieces in a study on ESWT, blinding of ESWT therapists can only be achieved when another person prepares the device before rESWT or sham treatment. This, however, is almost impracticable and has not been done in any of the more than 100 studies on rESWT and fESWT listed in the PEDro database (Schmitz et al., 2015). The solution to this issue is a strict, standardized way of interaction between the ESWT therapist and the patients, irrespective of treatment allocation (as mentioned in a study by Buchbinder et al., 2002). This approach will also be applied in the proposed study.
- All assessments before the first treatment (baseline) and during the follow-up period will be performed by assessors blind to the intervention.

5. Follow-up and statistical analysis

- Follow-up will be the same for all study patients.
- The design of the proposed study guarantees that there will be full compliance with the allocated treatment and, thus, no contamination of one group.
- The patient's age, gender, body mass index, job occupation and duration of non-specific low back pain are potential confounding factors when treating chronic non-specific low back pain with rESWT. Normal distribution of these data will be tested using the D'Agostino-Pearson omnibus test. In case of passing the normality test we will report mean and standard error of the mean of these variables; otherwise we will report inter-quartile ranges of these variables. Comparison between groups will be performed with ANOVA followed by Bonferroni post tests for pairwise comparisons in case of passing the normality test, or the nonparametric Kruskal-Wallis test followed by Dunns tests for pairwise comparisons in case of not passing the initial normality test.
- As outlined in Section "Primary clinical outcome and definition of treatment success" above, the primary clinical outcome will be the PSEQ score at 12 weeks after baseline. Treatment success (i.e., number of patients with individual improvement of PSEQ score by more than 20% at 12 weeks after baseline) will be tested with Fisher's exact test.
- As outlined in Section "Secondary clinical outcomes" above, the secondary clinical outcomes will be the NRS score, OLDPDQ score, PHQ-9 score, Cobb's angle, vertebral body and intervertebral disc wedging and facet joint angles. Each secondary clinical outcome will return a single data point at each time of follow-up examination. The NRS score, OLDPDQ score and PHQ-9 score are not normally distributed data. Accordingly, we will report inter-quartile ranges of these variables. Comparison between groups will be performed using the nonparametric Kruskal-Wallis test followed by Dunns tests for pairwise comparisons. Normal distribution of the Cobb's angle, vertebral body and intervertebral disc wedging and facet joint angles will be tested using the D'Agostino-Pearson omnibus test. Comparison between groups will be performed with ANOVA followed by Bonferroni post tests for pairwise comparisons in case of passing the normality test, or the nonparametric Kruskal-Wallis test followed by Dunns tests for pairwise comparisons in case of not passing the initial normality test.
- The probability value of less than 0.05 ($p\text{-value} < 0.05$) will be considered as statistically significant (Lang & Secic, 2006).

- All calculations will be performed using GraphPad Prism (version 5.00 for Windows, GraphPad Software, San Diego, CA, USA).
- All main conclusions of the study will be based on analyses of intention to treat rather than analyses of treatment. Note that there are various available methods for handling missing data in clinical trials (European Medicines Agency, 2010). In case of missing data (i.e., in case a patient will withdraw or will be lost during the treatment or the follow-up periods) we will determine together with the statistics experts at the Institute for Medical Informatics, Biometry and Epidemiology (IBE) at the Ludwig-Maximilians-University of Munich (Munich, Germany) the most appropriate method for performing analyses of intention to treat. After randomization and the first treatment with respectively rESWT plus C-E drugs, rESWT alone or C-E drugs alone, no patient will be replaced.
- All efforts will be made to keep the proportion of patients lost to follow-up too small to affect the main findings of the proposed study.
- Patient-centered care throughout the proposed study will ensure that no patients will be lost to follow-up, or the number of patients lost to follow-up will be so small that findings would be unaffected by their inclusion.
- We will report actual probability values for all outcomes except where probability values less than 0.001 are found.
- We will avoid any retrospective unplanned subgroup analysis and, thus, “data dredging”.

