between-group statistical comparisons, and reports of both point estimates and measures of variability. The design of the proposed study on rESWT for chronic non-specific low back pain considers all these aspects, except of the fact that patients and therapists will not be blinded (which is in principle not possible when comparing combined ESWT /C-E drug therapy with ESWT alone and C-E drug therapy alone).

[figure not shown]
4. Chalmers et al. (1981) – This assessment consists of two evaluation forms that include 29 individually scored items, allowing a maximum score of 100.
5. Downs and Black (1998) – This assessment includes 27 individually scored items, allowing a maximum score of 32.
6. The CONSORT statement (Schulz et al., 2010) – The CONSORT statement is intended to improve the reporting of RCTs, enabling readers to understand a trial's design, conduct, analysis and interpretation, and to assess the validity of its results.

The assessments of Chalmers et al. (1981), Downs and Black (1998) and Schulz et al. (2000) are very similar. However, Downs and Black (1998) provide the most specific questions. Accordingly, the design of the proposed study on rESWT for chronic non-specific low back pain was developed according to the criteria set out by Downs and Black (1998). The proposed study on rESWT for chronic non-specific low back pain will achieve a very high rating on the assessment by Downs and Black (1998).

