4.11. Outcome of Interest

4.11.1. Primary clinical outcome and definition of treatment success

- Primary clinical outcome will be the Pain Self-Efficacy Questionnaire (PSEQ) score (Nicholas, 1989).
 - Patients will be asked to rate how confident they are at the time of examination despite the presence of their pain in performing the following activities, listed by selecting a number on a 7 point scale where 0 equals “not at all confident” and 6 equals “completely confident”:
 - I can enjoy things, despite the pain.

- I can do most of the household chores (e.g. tidying-up, washing dishes, etc.), despite the pain.
- I can socialize with my friends or family members as often as I used to do, despite the pain.
- I can cope with my pain in most situations.
- I can do some form of work, despite the pain (“work” includes housework, paid and unpaid work).
- I can still do many of the things I enjoy doing, such as hobbies or leisure activity, despite the pain.
- I can cope with my pain without additional medication (next to rESWT plus C-E drugs, rESWT alone or C-E drugs alone, respectively).
- I can still accomplish most of my goals in life, despite the pain.
- I can live a normal lifestyle, despite the pain.
- I can gradually become more active, despite the pain.
- Scores on the PSEQ may range from 0 to 60, with higher scores indicating stronger self-efficacy beliefs.
- A point score change of 11 points for the PSEQ score corresponds to the minimal clinically important difference (MCID), defined as the smallest difference that patients and clinicians perceive to be worthwhile when treating chronic non-specific low back pain (Maughan and Lewis, 2010).
- According to Maughan and Lewis (2010) the PSEQ score is responsive to clinically important change over time.
- The PSEQ score will be collected at baseline and at all follow-up examinations, i.e., two weeks, four weeks, 12 weeks and 24 weeks after baseline.
- In the present study treatment success is defined as individual improvement of the PSEQ score by more than 20 points at 12 weeks after baseline.

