In summary, the proposed study has a power of more than 0.8 in finding a difference in treatment success (individual improvement of the PSEG score by more than 20 points at 12 weeks after baseline) between rESWT plus C-E drugs and C-E drugs alone, as well as between rESWT alone and C-E drugs alone, for treating chronic non-specific low back pain when randomizing at least 49 patients into each group.

On the other hand, the proposed study does not have a power of more than 0.8 in finding a difference in treatment success (individual improvement of the PSEG score by more than 20 points at 12 weeks after baseline) between rESWT plus C-E drugs and rESWT alone, for treating chronic non-specific low back pain when randomizing less than 134 patients into each group.

In summary, the proposed study can test the following hypotheses in the treatment of chronic non-specific low back pain: (i) rESWT plus C-E drugs is superior to C-E drugs alone, and (ii) rESWT alone is superior to C-E drugs alone. Furthermore, the proposed study can retrieve important pilot data for designing a follow-up study testing the hypothesis that rESWT plus C-E drugs is superior to rESWT alone in the treatment of chronic non-specific low back pain.

Collectively, the results of the Power analysis reinforce the validity of the proposed study protocol for testing efficacy and safety of rESWT using the Swiss DolorClast for chronic non-specific low back pain.

6. Patient protection procedures

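### Treatment success on the PSEQ is a gain of more than 20 points in sections 4.11.1 and 5.1 but more than 20% in the analysis text of section 5; the primary label and the planned PSEQ estimates also need settling.

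*Combined protocol and SAP*

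**What the plan says.** **Success rule.** Section 4.11.1 states that "treatment success is defined as individual improvement of the PSEQ score by more than 20 points at 12 weeks after baseline". The closing summary of section 5.1 uses the same rule, "individual improvement of the PSEG score by more than 20 points at 12 weeks after baseline" (PSEG is evidently PSEQ). Section 5, which refers back to section 4.11.1 and names the test, counts patients with "individual improvement of PSEQ score by more than 20% at 12 weeks after baseline".

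**Primary outcome.** Section 4.11.1: "Primary clinical outcome will be the Pain Self-Efficacy Questionnaire (PSEQ) score". Section 5 adds the time point: "the primary clinical outcome will be the PSEQ score at 12 weeks after baseline". The one PSEQ test that follows is Fisher's exact test on the number of successes. Every power and sample-size figure in section 5.1 is for a success proportion.

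**Scale and data.** "Scores on the PSEQ may range from 0 to 60", and section 4.11.1 gives 11 points as the minimal clinically important difference (MCID). "The PSEQ score will be collected at baseline and at all follow-up examinations". The eligibility criteria in sections 4.4 and 4.5 set no PSEQ limit.

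**Estimates.** Section 5 gives summary and comparison methods for the baseline factors and comparison methods for the secondary outcomes. For the PSEQ score it gives neither. It promises p-values; a confidence interval is mentioned only in section 5.1, as a way of stating the 5% error rate.

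**The concern.** The success rule decides which patients count as responders, and so what the main test compares. If the statistician follows section 5, the analysis uses a different threshold from the one that defines the endpoint and underlies the power statement. If the choice waits until the data are in, it can be made with knowledge of the results. That matters more here because patients and therapists are unblinded and the outcome is self-reported.

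The label adds to this. A reader of section 5 expects an analysis of the 12-week score and finds only a test of a proportion. With no planned estimate, the main result could be reported as a p-value with no effect size or interval.

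**Working it through.** **1. The plan's own figure.** Inputs from Table 9: 40% success on C-E drugs alone, 70% on rESWT alone, two-sided 5%, power 0.8. Fleiss formula:

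n = [1.960·√(2·0.55·0.45) + 0.842·√(0.4·0.6 + 0.7·0.3)]² / 0.30² = 41.97, so 42.

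With continuity correction, n/4·[1 + √(1 + 4/(n·0.30))]² = 48.41, so 49. Both match Table 9, and 49 is the figure in the summary of section 5.1. The same formulas for 70% against 85% give 121 and 134, matching Table 10. The sample-size arithmetic is right for a success proportion.

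**2. The two rules on the 0 to 60 scale.**

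| Baseline | More than 20 points | More than 20% of baseline | More than 20% of the range |
|---|---|---|---|
| 20 | score above 40 | gain above 4 | gain above 12 |
| 30 | score above 50 | gain above 6 | gain above 12 |
| 40 | above 60: impossible | gain above 8 | gain above 12 |

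No reading of 20% gives 20 points. The relative rule is attainable only when 1.2 × baseline is below 60, that is, baseline below 50, so its threshold is always under 10 points and below the stated MCID of 11. The 20-point rule is 20/11 = 1.8 times the MCID.

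**3. Power under the 20-point rule.** Exact Fisher power by enumerating all 51 × 51 tables, n = 50 per group, two-sided 5%, pairwise as in section 5.1:

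| Success rates | Power |
|---|---|
| 70% vs 40% (rate in the title of Table 9) | 83% |
| 70% vs 35% (rate in the text of section 5.1) | 93% |
| 85% vs 35% | about 100% |
| 85% vs 70% | 35% |

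The control rate is 35% in the text and 40% in the titles of Tables 7 and 9. The 49 per group rests on 40%. That is a separate inconsistency, but it fixes the starting point here at 83% or 93%.

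**4. Illustration of the effect of the rule.** The documents give no PSEQ SD, baseline or distribution, so these are assumptions: fixed baseline 20 or 30, normal change with SD s = 10 or 15, the same in each group. If a group has success rate p under the 20-point rule, its rate under a threshold t is Φ(z(p) + (20 − t)/s). For example, with t = 4, s = 10 and p = 0.35: Φ(−0.385 + 1.6) = 0.888.

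| Meaning of 20% | t | s | 35% becomes | 70% becomes | Fisher power |
|---|---|---|---|---|---|
| of baseline 20 | 4 | 10 | 88.8% | 98.3% | 29% |
| of baseline 20 | 4 | 15 | 75.2% | 94.4% | 70% |
| of baseline 30 | 6 | 10 | 84.5% | 97.3% | 46% |
| of baseline 30 | 6 | 15 | 70.8% | 92.8% | 77% |
| of the range | 12 | 10 | 66.1% | 90.7% | 82% |
| of the range | 12 | 15 | 55.9% | 85.5% | 88% |

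These compare with 93% under the 20-point rule. Starting from 40% instead of 35%, the same formula gives 15% to 58% for the relative reading and 65% to 75% for the range reading, against 83%. For 85% against 35% it gives 44% to 97% and 98% to nearly 100%. The cap at 60 alters none of these, since every threshold lies below 60.

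**The case against.** **The responder analysis is what is meant.** The heading of section 4.11.1 joins the primary outcome to the definition of success, section 5 names the score and Fisher's test in one bullet, and section 5.1 works only with proportions. This stands. A reader might infer that the trial has no prespecified primary test, or two rival ones. The documents do not support that: there is one PSEQ test and no competing score test. The mismatch is one of labelling, and one sentence repairs it.

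**Estimates are promised.** Section 4.1 says the design considers "between-group statistical comparisons, and reports of both point estimates and measures of variability", and it lists the Delphi item on estimates and variability for the primary outcome. These are general statements about quality scales. They name no PSEQ estimate and no interval.

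**The power loss is assumed.** This also stands. A reader might infer that the 20% rule leaves the trial underpowered. The steep falls need the relative-to-baseline reading and an assumed SD. With the range reading and a 35% control rate, power stays at 82% to 88%.

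**A score analysis would gain power.** A reader might infer this too, and it is not supported. For 85% against 70%, an uncapped normal model gives ANCOVA power of 79% to 88%, but it breaks the scale: 85% success at SD 10 implies a mean gain of 20 + 1.036·10 = 30.4, so a mean of 60.4 from baseline 30. Capping scores at 60 widens the range to about 54% to 88%. Section 5.1 treats that contrast as pilot data anyway, and Fisher's test already exceeds 80% for the two contrasts it says the study can test.

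**The ceiling may be minor.** The arithmetic at baseline 40 holds, but without a baseline distribution nobody can say how many patients it affects.

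**Conclusion.** The point holds. The contradiction between 20 points and 20% rests on the text and the 0 to 60 range alone; no assumption is needed. The power statement in section 5.1 applies to the 20-point rule, so running section 5 as written would test an endpoint for which no power has been calculated. The size of the power change cannot be fixed from the documents: for rESWT alone against C-E drugs alone, the illustrations run from 15% to 88%, depending on the meaning of 20%, the assumed SD and baseline, and the control rate.

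The primary label and the missing PSEQ estimate are lesser faults. The evidence points to a 12-week responder analysis; what is lacking is a sentence that says so and an effect estimate to go with the p-value. The sample-size calculation itself is not at fault on this point.

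**What to change.** 1. Use one success rule in sections 4.11.1, 5 and 5.1. If it is the 20% rule, say what the 20% is taken of, and restate the success rates and power in section 5.1 for it.
2. State that the success proportion at 12 weeks, on which section 5.1 is based, is the primary analysis by Fisher's exact test, and report pairwise risk differences with 95% confidence intervals. At 70% against 40% with 50 per group the interval would be about 0.30 ± 1.96·√(0.7·0.3/50 + 0.4·0.6/50) = 0.30 ± 0.19.
3. As a supportive analysis, prespecify the between-group difference in 12-week PSEQ score adjusted for baseline PSEQ, with 95% confidence intervals, and a rank-based sensitivity analysis because the score is bounded. Its purpose is estimation; claim no gain in power from it.

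Cost: wording in three sections and a little more analysis. No added patients, visits or measurements, since PSEQ is already collected at baseline and 12 weeks. The team should check that the GraphPad Prism version named in section 5 can fit the adjusted model, or name another program. If the 20% rule is kept, section 5.1 has to be recalculated.

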5.1. Power analysis

In none of the studies on ESWT for non-specific low back pain performed so far (Nedelka et al., 2014; Lee et al., 2014; Han et al., 2014; Moon et al., 2016) a definition of treatment success was defined, a Power analysis was reported and the PSEQ score was used to assess clinical outcome. Accordingly, these studies are only of very limited use for the purpose of performing a Power analysis of the proposed study.

Based on anecdotal evidence from several therapists in Europe and Latin America who have been using rESWT for non-specific low back pain for more than a decade we hypothesize that treatment of chronic non-specific low back pain with rESWT alone as described above will result in a success rate of approximately 70%, and the combination of rESWT and C-E drugs in a success rate of approximately 85%. Furthermore, based on our own experience we hypothesize that treatment of chronic non-specific low back pain with C-E drugs alone as described above will result in a success rate of only approximately 35%

On this basis we performed a Power analysis, both for a percentage of 35% as well as for various other percentages (ranging between 10% and 99.9%) of patients with treatment success when treated with C-E drugs alone, accounting for a two sided-confidence interval of 95% (and, thus, a type-1 error rate of 5%). Calculations were performed using the software Open Source Epidemiologic Statistics for Public Health (www.openepi.com). The results are summarized in Tables 7 and 8.

Table 7. Power for the proposed RCT on rESWT plus C-E drugs or rESWT alone for chronic non-specific low back pain, accounting for a two sided-confidence interval of 95% and a percentage of patients with treatment success of 40% when treated with C-E drugs alone (assuming n=50 patients per group).

Percent of patients treated with rESWT plus C-E drugs or C-E drugs alone with treatment success [%]	Power based on Normal approximation [%]	Power based on Normal approximation with continuity correction [%]
99.9	100	100
90	100	100
85	100	100
80	99.8	99.6
70	95.0	92.4
60	71.3	63.5
50	32.7	25.2
40	7.2	3.5
35	1.1	0

Table 8. Power for the proposed RCT on rESWT plus C-E drugs for chronic non-specific low back pain, accounting for a two sided-confidence interval of 95% and a percentage of patients with treatment success of 70% when treated with rESWT alone (assuming n=50 patients per group).

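### Section 5 tests treatment success as a PSEQ gain above 20% with no denominator, while Sections 4.11.1 and 5.1 define it as a gain above 20 points

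*Combined protocol and SAP*

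**What the plan says.** Section 4.11.1 makes the PSEQ score the primary outcome. It states that "Scores on the PSEQ may range from 0 to 60", gives 11 points as the minimal clinically important difference, and then fixes the responder rule: "treatment success is defined as individual improvement of the PSEQ score by more than 20 points at 12 weeks after baseline".

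Section 5.1 repeats that rule twice in its summary of power, as "individual improvement of the PSEG score by more than 20 points at 12 weeks after baseline" (printed there with PSEG for PSEQ).

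Section 5 (Follow-up and statistical analysis) names the primary outcome as the PSEQ score at 12 weeks, opening with "As outlined in Section 'Primary clinical outcome and definition of treatment success' above". Its next sentence assigns Fisher's exact test to treatment success and explains the term as the "number of patients with individual improvement of PSEQ score by more than 20% at 12 weeks after baseline". It does not say whether the percentage is of the patient's baseline score or of the scale range. No other test is given for the primary outcome.

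**The concern.** One responder endpoint has two definitions, and the odd one out sits beside the test. An analyst working from Section 5 meets an explicit threshold that differs from the one used to plan the trial, and it can be read in two ways. That gives three possible success counts from the same data.

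Two things are at stake:

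- If the wording is still open when outcomes are known, the definition could be chosen with the results in view.
- The assumed success rates in Section 5.1 (about 35% for C-E drugs, 70% for rESWT and 85% for the combination) lead to power conclusions worded for the points rule. Under a percent rule the plan states neither success rates nor power.

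**Working it through.** **1. The plan's own figure.** Section 5.1 concludes that 49 patients per group suffice. This is the Table 9 entry for 70% against 40% (two-sided 5%, power 0.8, Fleiss with continuity correction).

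- Uncorrected: n = [1.960·√(2·0.55·0.45) + 0.842·√(0.70·0.30 + 0.40·0.60)]² / 0.30² = (1.379 + 0.565)² / 0.09 = 41.97, so 42.
- Corrected: n' = (41.97/4)·[1 + √(1 + 4/(41.97·0.30))]² = 48.4, so 49.

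The same steps for 85% against 70% give 121 and 134. All four figures match Tables 9 and 10.

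**2. Exact thresholds.** Inputs from Section 4.11.1: whole-number scores from 0 to 60 and an 11-point minimal clinically important difference. For baseline b and gain g, success requires:

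- points rule: g > 20, so g ≥ 21, possible only if b + 21 ≤ 60, that is b ≤ 39;
- 20% of range: g > 0.2·60 = 12, so g ≥ 13, possible only if b ≤ 47;
- 20% of baseline: g > 0.2·b, possible only if b ≤ 49 (at b = 50 a gain of 11 is needed and only 10 remain); undefined as a percentage at b = 0.

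| Baseline | 20 points | 20% of range | 20% of baseline |
|---|---|---|---|
| 10 | 21 | 13 | 3 |
| 20 | 21 | 13 | 5 |
| 30 | 21 | 13 | 7 |
| 40 | not attainable | 13 | 9 |
| 45 | not attainable | 13 | 10 |
| 50 | not attainable | not attainable | not attainable |

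The baseline-percent rule asks for at most 10 points wherever it can be met, so it always lies below 11. Since 20% of baseline is at most 0.2·60 = 12 points, no baseline makes it agree with the points rule.

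**3. Nesting.** A gain above 20 points exceeds both 12 points and 0.2·b for every b. Each points-rule success is therefore also a success under either percent reading, and the percent count can only be equal or higher.

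**4. Illustration of size.** The documents give no PSEQ mean or SD, so this step rests on assumptions. Baseline was taken as normal with mean 15-25 and SD 8-13, and change as normal with SD 11. Scores were rounded and limited to 0-60. The mean change in each arm was set so that the points rule gives the hypothesised 35%, 70% and 85%. Fisher power is exact for n = 50 per arm, two-sided 0.05, no dropout.

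| | 20 points | 20% of range | 20% of baseline |
|---|---|---|---|
| Success, C-E drugs | 35% | 64-66% | 85-88% |
| Success, rESWT | 70% | 90-91% | 96-98% |
| Success, combination | 85% | 96-97% | 97-99.5% |
| Power, rESWT v C-E drugs | 93% | 82-86% | about 30-46% |
| Power, combination v C-E drugs | over 99% | 97-99% | about 41-69% |

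A lenient threshold makes nearly everyone a success, so the arms are harder to tell apart. The size depends heavily on the assumptions. With change SD 8-15 and a baseline mean of 30 added, rESWT v C-E power runs from about 1% to 77% under 20% of baseline and from about 47% to 92% under 20% of range.

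**The case against.** The strongest reply is that the document resolves this itself. The bullet in Section 5 sends the reader to 4.11.1, treatment success is a defined term there, and three statements in points stand against one in percent. That makes a slip the likely explanation. It does not remove the problem: the cross-reference introduces the sentence naming the primary outcome, and the following sentence gives its own, different explanation of success beside the test.

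A second reply is that the simulated power figures rest on distributions the plan does not supply. That is right. A range of 1% to 77% shows only that the loss could be anything from moderate to severe. Nor do baseline means of 15-25 bound the possibilities, which is why a mean of 30 was added. At that mean the 85% rate cannot be reached when the baseline SD is 10 or more, but the rESWT v C-E comparison needs only 35% and 70%.

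Third, the 35% anchor is not the only control rate in the plan. The text of Section 5.1 hypothesises 35%, while Table 9, the source of the 49 per group, uses 40%. At 70% against 40% with 50 per arm, Fisher power under the points rule is 83%, not 93%. This changes the reference value but not the contradiction.

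Finally, Section 5 names the PSEQ score at 12 weeks as the primary outcome, and treatment success is its dichotomised form. That is so, but the dichotomised form is the one that is tested and powered.

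**Conclusion.** The contradiction is real and uncorrected, and it concerns the only form of the primary outcome that has a specified test. The firm results need only the 0-60 scale and whole-number scores: minimum gains of 21, 13 and 1-10 points under the three readings, the last always below the protocol's 11-point minimal clinically important difference, and nested success counts. That power is unstated under a percent rule holds only if percent is the operative rule. The simulated rates and powers show direction and a possible size, and do not predict this trial's data. The points reading is very probably the intended one. The text must still be made single-valued, because it sets the threshold for the primary test.

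**What to change.** Before any outcome data are seen, change more than 20% to more than 20 points in the treatment-success sentence of Section 5, so that it agrees with Sections 4.11.1 and 5.1. This is one phrase. It needs no extra patients, visits or data, and the planned sizes (49 and 134 per group) stay as stated.

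If a percentage is truly intended, name its denominator in Sections 4.11.1, 5 and 5.1. For a percentage of baseline, also say how a baseline of zero is handled. The assumed success rates and the sample size would then have to be justified again for that rule.
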